10.3 Vital Signs, Physical Findings, and Other Observations Related to Safety

10.3.1 Vital Signs and Physical Findings

The following vital signs measurements will be obtained:

- Pulse rate
- Systemic and diastolic blood pressure
- Temperature (oral, tympanic, or axillary)

A summary of participants who meet each of the Marked Abnormality (MA) Criteria (Appendix 13.3) will be summarized by treatment group at each timepoint.

A by-participant listing of all vital sign measurements and change from Baseline will be presented by treatment group and timepoint. The listing will include a flag for values identified as MA criteria (Appendix 13.3).

Repeated and unscheduled measurements will be handled as described in Section 4.3.

10.4 12-lead Electrocardiograms (ECG)

12-Lead ECG data (measured values and changes from Baseline) will be listed only. The following variables will be reported:

- Heart rate
- PR interval
- RR interval
- QRS duration
- QT interval
- QT corrected for heart rate using Bazett's formula ($QTcB = QT/RR^{1/2}$)
- QT corrected for heart rate using Fridericia's formula ($QTcF = QT/RR^{1/3}$)

A summary of participants who meet each of the Market Abnormally (MA) criteria outlined in Appendix 13.4 will be summarized by treatment group at each timepoint and overall.

All calculations of changes from Baseline will be based on the mean of triplicate assessments at each timepoint. If there are not 3 available measurements at a given timepoint, the mean will be calculated based on the number of measurements for which data are provided.

Electrocardiogram findings for the individual triplicate measurements will be listed separately.

Repeated and unscheduled measurements will be handled as described in Section 4.3.

10.5 Clinical Safety Laboratory Assessments

Laboratory data (as specified in Table 10-1 Protocol-required safety laboratory assessments in the protocol) and changes from Baseline (if applicable) for numeric variables will be listed by treatment group and timepoint. Values outside the reference range for the numeric variables will be flagged in the listings. The reference ranges will also be reported in the listings. In addition, the listings will include a flag for values identified as Laboratory assessments – MA Criteria (Appendix 13.2).

Measurements BLQ will be imputed with half of the LLOQ for the purpose of calculating change from Baseline. Measurements ALQ, if applicable, will be imputed to the upper quantification limit. These rules will be applied to all safety laboratory data including clinical chemistry and urinalysis.

Descriptive statistics will be calculated if at most 1/3 of the individual data points at a time point are missing or are either not quantifiable (<LLOQ) or ALQ. Values that are BLQ will be replaced by the numerical value of the LLOQ/2 in this instance and values that are ALQ will be imputed to the value of the upper quantification limit. If more than two-thirds of the individual data points at a timepoint are missing or not quantifiable (BLQ and/or ALQ), no descriptive statistics will be calculated.

The following summaries/tables will be created:

- A summary of participants who meet each of the Laboratory assessments – MA criteria (Appendix Section 13.2) will be summarized by treatment group at each timepoint.

A listing for laboratory assessments will be also created using the SS.

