8.2.4 Clinical safety laboratory assessments

See Appendix 2, Section 10.2 for the list of clinical laboratory tests to be performed and to the Schedule of Activities (Section 1.3) for the timing and frequency.

The investigator must review the laboratory report, document this review, and record any clinically relevant changes occurring during the study in the AE section of the eCRF. The laboratory reports must be filed with the source documents. Clinically significant abnormal laboratory findings are those which are not associated with the underlying disease, unless judged by the investigator to be more severe than expected for the participant's condition.

All laboratory tests with values considered clinically significantly abnormal during participation in the study should be repeated until the values return to normal or Baseline or are no longer considered clinically significant by the investigator or Medical Monitor.

If such values do not return to normal/Baseline within a period of time judged reasonable by the investigator, the etiology should be identified, and the sponsor notified.

All protocol-required laboratory assessments, as defined in Appendix 2, Section 10.2, must be conducted in accordance with the laboratory manual and the Schedule of Activities.

If laboratory values from nonprotocol specified laboratory assessments performed at the institution's local laboratory require a change in participant management or are considered clinically significant by the investigator (eg, SAE or AE or dose modification), then the results must be recorded in the eCRF.

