4.3 Handling of repeated and unscheduled measurements

All repeated and unscheduled measurements will be presented in the listings, where applicable. The following general rules will apply to all repeated and unscheduled measurements:

- For repeated or unscheduled measurements obtained prior to the first dose of IMP the latest reliable value (which may be scheduled or unscheduled) will be used in the calculation of descriptive statistics (ie, Screening and/or Baseline)
- For repeated or unscheduled measurements obtained at the designated Baseline visit, the latest reliable value (which may be scheduled or unscheduled) will be defined as the Baseline record if occurred prior to the first dose of IMP
- If any scheduled measurement obtained at any time point after the first dose of IMP is missing, unscheduled measurements will not be used for any missing assessment.
- See Section 10.4 for the rules applied to ECG triplicate measurements.

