13.4 Electrocardiogram (ECG) – Abnormal

Abnormality criteria to be applied in the assessment of ECG parameter values are given below:

Parameter	Abnormality Criteria
QT interval (ms)	$\geq 500\text{ms}$
	$\geq 60\text{ms}$ increase from Baseline
QTc(F) (ms)	$\geq 500\text{ms}$
	$\geq 60\text{ms}$ increase from Baseline
PR interval (ms)	Treatment-emergent value $> 200\text{ms}$
QRS interval (ms)	Treatment-emergent value $> 100\text{ms}$
Heart rate (bpm)	$< 50\text{bpm}$
	$> 120\text{bpm}$

Abbreviations: BL= Baseline, bpm = beats per minute; ms = milliseconds; QTc(F) = Fridericia corrected QT interval;

Note: Treatment-emergent is defined as meeting the criteria at any post-Baseline visit during the Treatment Period (including unscheduled visits) and not meeting the same criteria during Baseline

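### The laboratory and vital-sign marked-abnormality tables have no overall count, so participants abnormal only at an unscheduled test probably appear in no cell

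*SAP*

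**What the plan says.** **Laboratory values.** The one table listed in SAP 10.5 counts participants meeting the marked-abnormality "criteria (Appendix Section 13.2) will be summarized by treatment group at each timepoint".

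**Vital signs.** SAP 10.3.1 has the same form: "Criteria (Appendix 13.3) will be summarized by treatment group at each timepoint".

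**ECG.** SAP 10.4 goes further. Participants meeting the criteria "outlined in Appendix 13.4 will be summarized by treatment group at each timepoint and overall". A note in Appendix 13.4 defines treatment-emergent as "meeting the criteria at any post-Baseline visit during the Treatment Period (including unscheduled visits" being counted too.

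**Timepoints and unscheduled values.** SAP 3.2.1 analyses all data by the visits in the Schedule of Activities and applies no visit windows. SAP 3.2.3 maps only Early Withdrawal assessments to a scheduled visit. SAP 4.3 presents repeated and unscheduled values in the listings and adds that, after the first dose, "unscheduled measurements will not be used for any missing assessment".

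**Other outputs.** SAP 3.9 item 11 drops the change-from-Baseline analyses for vital signs and laboratory data and leaves raw listings. Under SAP 10.3.1 and 10.5 those listings flag every value that meets a marked-abnormality criterion.

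**Why off-schedule tests occur.** Protocol 8.2.4 states: "All laboratory tests with values considered clinically significantly abnormal during participation in the study should be repeated until the values return to normal". Protocol section 8 also allows Unscheduled Visits, for example for an adverse event, with vital signs, hematology, biochemistry and IgG.

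**The concern.** The basic safety question for a marked abnormality is how many participants in each arm ever had one. A table that stops at separate timepoints does not answer it, for two reasons.

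First, a value measured between scheduled visits belongs to no timepoint. Off-schedule testing is prompted by illness or by an abnormal earlier result, so it is a likely place for a marked value to appear. If such values have no cell, the table tends to understate acute abnormalities.

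Second, the same person may be counted at several timepoints, so the cells do not add up to people.

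Safety and tolerability are the secondary objective, and formal efficacy testing has been dropped after early termination. Clear safety counts are therefore a larger share of what the report can offer.

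**Working it through.** There is no planned figure to reproduce; the point concerns how tables are specified. The check sets the passages side by side.

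**1. Is there an overall count?**

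| Domain | By timepoint | Overall | Criteria text mentions unscheduled visits |
|---|---|---|---|
| Laboratory (SAP 10.5, 13.2) | yes | no | no |
| Vital signs (SAP 10.3.1, 13.3) | yes | no | no |
| ECG (SAP 10.4, 13.4) | yes | yes | yes, in the treatment-emergent note |

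The treatment-emergent note in 13.4 has limited reach. Only the PR and QRS criteria use that term; the QT, QTcF and heart-rate criteria do not. What ECG offers as a clear precedent is the overall count.

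**2. Does an unscheduled post-dose value have a cell?** The steps are: analysis is by scheduled visit (3.2.1); no window moves a value to a neighbouring visit (3.2.1); only Early Withdrawal data are remapped (3.2.3); unscheduled values go to listings and cannot stand in for a missing visit (4.3). Nothing is left that would place the value in a by-timepoint table. This is an inference, because no sentence says that such a value is left out of the abnormality counts.

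**3. Repeats at the same post-dose visit.** SAP 4.3 says which value to use before the first dose and at Baseline. It gives no rule for repeats after dosing, so two programmers could fill the same cell differently.

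**4. Can the cells be added up?** Let c(t) be the number in an arm meeting a criterion at scheduled timepoint t. The number E who met it at any scheduled timepoint satisfies only

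max c(t) ≤ E ≤ sum of c(t).

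One participant at each of two timepoints gives c = 1 and c = 1, so E may be 1 or 2. Participants abnormal only off schedule come on top of E.

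**5. A constructed example.** Suppose ALT is 4×ULN at one scheduled visit, 6×ULN at an unscheduled test and 2×ULN at the next scheduled visit. The criterion in 13.2.2 is above 5×ULN. Only the unscheduled value meets it, so on the reading in step 2 both by-timepoint cells show zero for this participant.

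**6. What one participant weighs.** SAP 2.3 gives 33 randomized, at 2:1. The actual split is not stated; taking it as 33 × 2/3 = 22 and 33 × 1/3 = 11, one participant is 1/22 = 4.5% of the rozanolixizumab arm or 1/11 = 9.1% of placebo. This gives the scale of one missed case and is not an estimate of how many would be missed.

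**7. Do other outputs supply the count?**
- Total IgG is summarized as concentrations by time point (SAP 9.3.1), not as participants at or below the 1 g/L criterion.
- The liver-injury summary (SAP 10.5.1) uses an at-least-one-visit count, but its criteria need raised bilirubin together with raised AST or ALT. An isolated high ALT would not qualify. The wording says the summary was planned, so its status is unclear.
- SAP 10.5 keeps a rule for when descriptive statistics may be calculated, but lists no table of them.

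**The case against.** The best case for leaving the plan alone has four parts.

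**The data remain visible.** Every marked value is flagged in listings that include unscheduled results, and there are only 33 participants. A reader might infer that the report could not establish how many participants ever met a criterion; that is not supported, since a hand count would give it. What is missing is a tabulated figure.

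**The exclusion is not written down.** A reader might infer that SAP 4.3 expressly removes unscheduled and repeat values from these tables. It does not. Its one express post-dose rule is that unscheduled values do not replace missing scheduled ones. SAP 10.4 also points to 4.3 and still has an overall count, which suggests the authors did not see 4.3 as an obstacle. This stands, and it is why step 2 is called an inference. It also means the text should be made explicit.

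**Adverse-event tables catch some cases.** Clinically relevant laboratory changes are recorded as adverse events (Protocol 8.2.4). Most laboratory criteria correspond to CTCAE Grade 3 or higher (SAP 13.2), and the overview counts participants with such events (SAP 10.2.2). This helps in part only: the overview does not identify the parameter, and hypogammaglobulinemia is kept out of adverse-event recording (Protocol 8.3).

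**An any-value count is not neutral.** Unscheduled tests are triggered by the investigator, so the count rises with testing intensity. This is true and calls for a footnote. It does not argue for having no such count.

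**Conclusion.** The point holds as a minor one. The laboratory and vital-sign tables lack the overall count that ECG has; their cells cannot be summed to participants; and a post-dose abnormality seen only at an unscheduled test would, on the natural reading of SAP 3.2.1 with 4.3, appear in none of them. They are the main tabulated count against these criteria, but not the only information on these data.

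The size is unknown. It is tempting to measure it from the gaps between laboratory visits in Protocol Table 1-4, but that is the Amendment 3 schedule and SAP section 1 states that nobody was randomized under it. The earlier schedules are not shown. Some prompts for extra testing, such as the ad hoc IgG footnote, are also new in Amendment 3. The repeat-testing instruction in Protocol 8.2.4 is not listed as changed in the amendment history shown, so it is assumed to have applied.

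No efficacy or confirmatory conclusion depends on this.

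**What to change.** - In SAP 10.3.1 and 10.5, add a row for any post-Baseline value, including unscheduled and repeat measurements, counting each participant once per criterion and arm. It can be shown by Treatment and Safety Follow-up Period, in line with SAP section 10.
- In SAP 4.3, state that the bar on unscheduled values concerns by-visit statistics only, and say which value is used when a post-dose visit has repeats.
- Add a footnote that the overall count partly reflects how often participants were tested off schedule.

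The cost is a few sentences in the SAP and one row per table, programmed from values already collected and flagged.

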10.5.1 Potential Drug-Induced Liver Injury

Data from subjects with any of the laboratory results meeting the criteria for potential drug-induced liver injury (PDILI) (below) was planned to be summarized by treatment arm and visit using the SS to include:

- Subjects with at least one post-Baseline liver laboratory assessment
- Incidence of potential hepatotoxicity with symptoms potentially associated with hepatitis or hypersensitivity, which will account for the number and percentage of subjects meeting laboratory criteria for PDILI for at least 1 visit and reporting at least 1 symptom potentially associated with hepatitis or hypersensitivity according to the Investigator on the PDILI CRF)
- Incidence of potential hepatotoxicity with no symptoms potentially associated with hepatitis or hypersensitivity, which will account for the number and percentage of subjects meeting laboratory criteria for PDILI for at least 1 visit and not reporting any symptom potentially related to hepatitis or hypersensitivity according to the Investigator on the PDILI CRF
- Number and percentage of study participants who meet the Laboratory criteria for PDILI (see table below)

Table 10-2: Laboratory criteria for PDILI

Laboratory Criteria	Comments
(AST or ALT > 3 x ULN) and TBL > 1.5 x ULN	- All values must be met at the same sample taken from the same visit
(AST or ALT > 3 x ULN) and TBL > 2 x ULN	
(AST or ALT > 3 x ULN) and TBL > 2 x ULN and ALP < 2 x ULN	- All values must be met at the same visit - Subjects who potentially meet Hy's law criteria at least 1 time during exposure. To be counted as potential Hy's Law, all criteria must be met at the same sample taken at the same visit.

ALP = Alkaline phosphatase; ALT = Alanine aminotransferase; AST = Aspartate aminotransferase; TBL = total bilirubin; ULN = upper limit of normal range.

A listing will be created only for visits for which at least one of the above criteria was fulfilled for a given participant and will display all results obtained at that visit for the specified parameters. The listing will specify AST, ALT, TBL, and ALP.

10.6 Concentrations of Total Protein and Albumin

Concentrations of total protein and albumin for each visit (as described in the schedule of events in the protocol) will be listed using the SS.

10.7 Serum and Plasma Complement Levels

Serum (C3 and C4) and plasma (C3a and C5a) complement variables will be listed by treatment group and time point.

Measurements below the limit of quantification (BLQ) will be imputed with half of the lower limit of quantification (LLOQ). Measurements above the limit of quantification (ALQ), if applicable, will be imputed to the upper limit of quantification.

All analyses described in this section will be performed on the SS.

10.8 Other Safety Variables

10.8.1 Physical examination

Results of physical examination abnormalities will be listed.

10.8.2 Pregnancy testing

Pregnancy testing will consist of serum testing at the Screening. The pregnancy test will be urine at all other visits.

A by-participant listing of the pregnancy test data will be provided by treatment group.

10.8.3 Childbearing potential

Childbearing potential will be collected at Screening. A by participant listing will be provided using the RS.

10.8.4 Assessment and management of Tuberculosis

Results of the interferon-gamma release assay tuberculosis (TB) test will be listed.

Results of the chest X-ray for TB will be listed.

Results of TB signs and symptoms questionnaire will be listed.

11 OTHER ANALYSES

11.1 Specific analyses for Pharmaceuticals and Medical Devices Agency (PMDA)

Separate summaries will not be presented for Japanese participants.

11.2 Headache questionnaire

The results of the headache questionnaire will be listed for each participant. No summary tabulations will be provided for these assessments.

13 APPENDICES

13.1 AE of focus (AEOF) for the Rozimab Program

AEOF Version: 3.0 or later, Date: 13Dec2021 will be used in this SAP as described below. In addition, worsening thrombocytopenia and haemorrhagic events will be included as AEOF as described in AEOF Version 1.4:

ARTICLE I. MedDRA 22.0 and 22.1 and 23.0 and 23.1 AND 24.0

The purpose of this document is to detail the approach to identifying TEAEs meeting criteria for AEs of focus (AEOF) for the Rozanolixizumab (also called Rozimab) program

The document is organized by MedDRA version. At the time of writing this document, MedDRA version 22.0 was planned to be used for all indications under investigation (MG, ITP, CIDP, HV). As there is no change between 22.0 and 22.1 and 23.0 and 23.1 and 24.0 regarding terms used in below selection criteria, all below specified algorithms apply to these Meddra versions. If future studies are planned which use a different (more recent) version of MedDRA, this document will be updated.

The MedDRA SMQ files version 22.0, 22.1, 23.0 and 23.1 are attached in the original document.

MedDRA SMQ file 24.0:

SMQ_spreadsheet_24_0_English.xlsx

Following Events are Adverse Event of focus For Rozanolixizumab for all indications:

No	Event (also included in Title of TFL output)	Selection criteria	Purpose CSR/ SSD/ IB
1	Headache (Note: also included in AESM if severe)	TEAE with HLGT='Headaches'	CSR/ SSD/ IB
2	Gastrointestinal disturbances (Note: also included in AESM if severe)	TEAE with HLT='Gastrointestinal and abdominal pains (excl oral and throat)' or HLT='Gastrointestinal signs and symptoms NEC' or HLT='Nausea and vomiting symptoms' or HLT='Diarrhoea (excl infective)' or HLT='Gastritis (excl infective)'	CSR/ SSD/ IB
3	Hypersensitivity reactions	SMQ='Hypersensitivity'	CSR/ SSD/ IB
4	Anaphylactic reactions	SMQ='Anaphylactic reaction' and	CSR/ SSD/ IB

		
TEAEs that either emerged on the same day as when a study medication injection reaction was received, or that emerged one day after a study medication injection was received, and which fulfill any of the following 3 criteria should be included in the summary table:
 
 1. If a subject reports any TEAE which codes to a PT included in Category A, then the event will be flagged as an anaphylactic reaction. 2. If a subject reports any TEAE which codes to a PT included in Category B AND reports any TEAE which codes to a PT included in Category C, and both TEAEs have the same start date, then both events will be flagged as anaphylactic reactions. 3. If a subject reports any TEAE which codes to a PT included in Category D AND reports (either a TEAE which codes to a PT included in Category B OR a TEAE which codes to a PT included in Category C), and both TEAEs have the same start date, then both events will be flagged as anaphylactic reactions. 	
5	Injection site reactions	TEAE with HLT='Injection site reactions' or HLT='Infusion site reactions' or HLT='Administration site reactions NEC'	CSR/SSD/ IB
6	Infusion Reactions	Infusion reaction marked on AE CRF page	CSR/SSD/ IB
7	Infections	TEAE with SOC ="Infections and infestations" Note: This was added as a reminder for safety that infections are considered as AE of focus and require assessment. No programming of this topic is required as TEAEs can be found in general AE Tables.	
8	Opportunistic infections	Opportunistic infections (including tuberculosis) will be summarized in a stand-	CSR/SSD/ IB

	
(Note: also included in AESM)
	
alone table using UCB-defined search criteria. Opportunistic infections are identified in two steps using the attached spreadsheet for MedDRA v24.0:
  
OI_MedDRA24_0.xls x
 
Step 1: Refer to column B of the spreadsheet which identifies the Preferred Terms (PTs) to be classified as opportunistic infections using either a single 'x' or a double 'xx'
 
 • TEAEs which code to a PT flagged with a single 'x' need to also be serious in order to be considered an opportunistic infection. • All TEAEs which code to a PT flagged with a double 'xx' are considered to be an opportunistic infection, regardless of seriousness. 
All serious TEAEs in the study database which code to a PT flagged with a single 'x' and all TEAEs in the study database which code to a PT flagged with a double 'xx' will be summarized as an opportunistic infection in the stand-alone table. [CQ97NAM= 'Opportunistic Infection - Automatic']
 
Step 2: Refer to column C of the spreadsheet which identifies the PTs that need to be evaluated on a case-by-case basis by the study physician and safety physician in order to determine whether it is a true opportunistic infection or not. The process for physician review is as follows:
 
 1. Study programming team creates a spreadsheet which lists all of the subjects with a TEAE present in the database which codes to a PT identified as case-by-case. [CQ98NAM= Opportunistic Infection - Manual Review Candidate] 	
--	--------------------------------------	--	--

		
Information from the AE dataset to be included in the spreadsheet: Subject ID, AE verbatim term, System Organ Class (SOC), High Level Term (HLT), Lower Level Term (LLT), PT, AE start date, AE end date, seriousness, severity, relationship to study medication, action taken. Additionally, a column will be included where the study physician/safety physician can document their decision on the case.
 
2. Study physician/safety physician (SPs) reviews the cases in the spreadsheet separately and reconciles final decision, and indicates in the additional column which AEs are confirmed to be opportunistic infections via a single 'x'.3. Study programming team incorporates these decisions into the AE dataset by merging the SPs decisions for individual subjects / PTs and flagging both the automatic and the confirmed opportunistic infections as such in the dataset. [CQ99NAM= 'Opportunistic Infection – Adjudicated'] 
The SPs reviews the context of all of a subject's data (AEs and possibly other) and concludes individually. Indicators of relevant cases may be e.g. repetitive occurrences, conjunction of other events or findings considered relevant. All subjects with a case-by-case PT reported that has been confirmed by the SPs to be an OI will be summarized as such in the stand-alone table, along with all of the events identified in Step 1 of this process. [CQ99NAM= 'Opportunistic Infection – Adjudicated'] The timing and frequency of Step 2 should be outlined and agreed to by the study team at the beginning of the study. It is suggested that this process be executed multiple times
	
--	--	--	--

This document cannot be used to support any marketing authorization application and any extensions thereof.

		
throughout the course of the study, more frequently in the weeks leading up to database lock, and one final time immediately prior to database lock.
 
Following the initial physician review of case-by-case events, subsequent reviews will be based on the cumulative set of case-by-case events present in the database at each time point of spreadsheet creation.
 
Physician decisions from previous runs should be retained in each subsequent run. The final run of the spreadsheet, with all SP decisions on the full set of case-by-case events, will be archived at the conclusion of the study analysis prepared for agency submission.
	
9	Reductions in albumin and plasma proteins	TEAEs with PT='Blood albumin decreased' or PT='Protein albumin ratio' or LLT='Plasma protein abnormal' or LLT='Protein serum plasma low'	CSR/ SSD/ IB
10	Effects on the kidney	TEAEs in SMQ='Acute renal failure'	CSR/ SSD/ IB
11	Drug related hepatic disorders	TEAEs in SMQ='Drug related hepatic disorders - comprehensive search'	CSR/ SSD/ IB
12	Effect on lipids	TEAEs with PT='Blood cholesterol increased' or PT='Low density lipoprotein increased' or PT='Blood triglycerides increased' or PT='Hypercholesterolaemia' or PT='Hypertriglyceridaemia' or PT='Hyperlipidaemia' or PT='Dyslipidaemia' or PT='Lipids increased'	CSR/ SSD/IB
ITF specific output			
13	Thromboembolic events	Embolitic and thrombotic events (SMQ)	CSR/ SSD/ IB
14	Worsening thrombocytopenia *	Haematopoietic thrombocytopenia (SMQ)	
15	Haemorrhagic events *	Haemorrhages (SMQ)	

* Data will be summarized by period and listed after adjudication of those events have been properly investigated

